**Notes for Generating the Actual Table:**

- Please use CPPar1 template
- Per study design needs, the following changes are made to this table relative to Celerion standard: columns <Treatment Sequence> and <Study Period> will be removed.
- PK Parameters will be presented in the following order and with following units: AUC0-t <ng\*hr/mL>, AUC0-inf <ng\*hr/mL>, AUC%extrap <%>, Cmax <ng/mL>, Tmax <hr>, Kel <1/hr>, T1/2 <hr>, CL <L/hr>, Vss <L>
- n will be presented as an integer (with no decimal);
- Exposure parameters (i.e. AUCs, Cmax, Vss, CL) will be presented with, at maximum, the precision of the bio data, and, at minimum, 3 significant figures (to be determined by the PKist once bio data are received).
  - Summary statistics will be presented with respect to the precision of the bio data: Mean, Median, and Geom Mean = +1; SD and SEM = +2, Minimum and Maximum = +0.
- Time parameters (i.e. Tmax, t1/2) will be presented with 2 decimals.
  - Summary statistics will be presented with respect to the number of decimals: Mean, Median, and Geom Mean = +1; SD and SEM = +2, Minimum and Maximum = +0.
- Values for rate constants (i.e. Kel) will be presented with 3 significant figures.
  - Summary statistics for Kel will be presented as: Mean, Median, and Geom Mean = +1; SD and SEM = +2, Minimum and Maximum = +0.
- CV% and Geom CV% for all parameters will be presented with 1 decimal

Program: /CAXXXX/sas\_prg/pksas/pk-tables.sas DDMMYYYY HH:MM  
Program: /CAXXXX/sas\_prg/pksas/adam\_pkparam.sas DDMMYYYY HH:MM

Table 14.2.1.1.6 will be in the following format:

Table 14.2.1.1.6 Intervals (Hours) Used for Determination of Plasma Xisomab 3G3 Kel Values (Pharmacokinetic Population)

Subject Number	Treatment	Interval	R2	n
X	0.25 mg/kg	XX.X - XX.X	X.XXX	X
X	0.5 mg/kg	XX.X - XX.X	X.XXX	X
X	x	XX.X - XX.X	X.XXX	X
X	X	XX.X - XX.X	X.XXX	X
X	X	XX.X - XX.X	X.XXX	X
X	X	XX.X - XX.X	X.XXX	X

0.25 mg/kg: Single IV Infusion of 0.25 mg/kg xisomab 3G3  
 0.5 mg/kg: Single IV Infusion of 0.5 mg/kg xisomab 3G3

R2 = Coefficient of determination  
 n = Number of points used in Kel calculation  
 . = Kel value not reportable.

---

**Notes for Generating the Actual Table:**

- Please use CPKel1 template
- Per study design, the "Treatment Sequence" column will be replaced with "Treatment" and the data will be presented vertically instead of horizontally.
- Interval start and stop times will be presented to 1 decimal or 3 significant figures minimum
- R2 will be presented to 3 decimals
- n will be presented as an integer

Program: /CAXXXX/sas\_prg/pksas/kel-tables-xover.sas DDMMYYYY HH:MM  
 Program: /CAXXXX/sas\_prg/pksas/adam\_kel.sas DDMMYYYY HH:MM

Aronora, Inc.  
 xisomab 3G3, Protocol 3G3-18-02  
 Celerion, Clinical Study Report No. CA23900

Tables 14.2.2.1.1 through 14.2.2.1.3, 14.2.3.1.1 through 14.2.3.1.3 will have the following format:

Table 14.2.3.1.1 Individual and Mean Difference Between Pre- and Post-dialysis Potassium Values (unit) - Days -7 to 12 - 0.25 mg/kg Xisomab 3G3 on Day 1 (Safety Population)

Subject Number	Day	0.25 mg/kg			0.5 mg/kg			Placebo		
		Pre- dialysis (units)	Post- dialysis (units)	Difference (units)	Pre- dialysis (units)	Post- dialysis (units)	Difference (units)	Pre- dialysis (units)	Post- dialysis (units)	Difference (units)
X	-7	XXX	X.XX	XXX	XXX	XX.X	X.XXX	XXX	XX.X	X.XXX
X	-7	XX.X	X.XX	XXX	XXX	XX.X	X.XXX	XXX	XX.X	X.XXX
X	-7	XX.X	X.XX	XXX	XXX	XX.X	X.XXX	XXX	XX.X	X.XXX
X	-7	X.XX	X.XX	XXX	XXX	XX.X	X.XXX	XXX	XX.X	X.XXX
X	-7	XXX	X.XX	XXX	XXX	XX.X	X.XXX	XXX	XX.X	X.XXX
n		XX	XX	XX	XX	XX	XX	XX	XX	XX
Mean		XXX.X	X.XXX	XXX.X	XXX.X	XX.XX	X.XXXX	XXX.X	XX.XX	X.XXXX
SD		XX.XX	XX.XX	XX.XX	XX.XX	XX.XX	XX.XX	XX.XX	XX.XX	XX.XX
CV%		XX.X	XX.X	XX.X	XX.X	XX.X	XX.X	XX.X	XX.X	XX.X
SEM		XX.XX	XX.XX	XX.XX	XX.XX	XX.XX	XX.XX	XX.XX	XX.XX	XX.XX
Minimum		XX.X	X.XX	XXX	XXX	XX.X	X.XXX	XXX	XX.X	X.XXX
Median		XX.XX	X.XXX	XXX.X	XXX.X	XX.XX	X.XXXX	XXX.X	XX.XX	X.XXXX
Maximum		XXX	X.XX	XXX	XXX	XX.X	X.XXX	XXX	XX.X	X.XXX

0.25 mg/kg: Single IV Infusion of 0.25 mg/kg xisomab 3G3

0.5 mg/kg: Single IV Infusion of 0.5 mg/kg xisomab 3G3

Placebo = pooled placebo

Difference = Pre-dialysis - Post-dialysis

Single IV infusion of 0.25, 0.5 mg/kg xisomab 3G3 or placebo was administered on Day 1

**Programmer Notes:**

For the BUN Tables 14.2.2.1.1 through 14.2.2.1.3 values will be reported at pre- and post-dialysis on Days -7, -5, -3, 1, 3, 5, 6, and 12. The screening values to be reported if not presented in other tables.

Aronora, Inc.  
xisomab 3G3, Protocol 3G3-18-02  
Celerion, Clinical Study Report No. CA23900

---

For the BUN Tables 14.2.2.1.1 through 14.2.2.1.3, additional column of "URR" will be reported at the right of the "Difference" column (as per Table 11-3 shell), with the following footnotes:

- Difference = Pre-dialysis - Post-dialysis
- Single IV infusion of 0.25, 0.5 mg/kg xisomab 3G3 or placebo was administered on Day 1
- $URR = (1 - (\text{post-dialysis BUN} / \text{pre-dialysis BUN})) * 100$

Program: /CAXXXX/sas\_prg/pksas/xxxxxxxx.sas DDMMYYYY HH:MM  
Program: /CAXXXX/sas\_prg/pksas/xxxxxxxx.sas DDMMYYYY HH:MM

Aronora, Inc.  
 xisomab 3G3, Protocol 3G3-18-02  
 Celerion, Clinical Study Report No. CA23900

Tables 14.2.5.1.7 through 14.2.5.1.9, 14.2.4.1.1 through 14.2.4.1.3 will have the following format:

Table 14.2.5.1.7 Individual and Mean Difference Between Pre- and Post-dialysis aPTT Values (unit) - Days -7 to 12 - 0.25 mg/kg Xisomab 3G3 on Day 1 (Safety Population)

Subject Number	Day	0.25 mg/kg			0.5 mg/kg			Placebo		
		Pre- dialysis (units)	Post- dialysis (units)	Fold Change (units)	Pre- dialysis (units)	Post- dialysis (units)	Fold Change (units)	Pre- dialysis (units)	Post- dialysis (units)	Fold Change (units)
X	-7	XXX	X.XX	XXX	XXX	XX.X	X.XXX	XXX	XX.X	X.XXX
X	-7	XX.X	X.XX	XXX	XXX	XX.X	X.XXX	XXX	XX.X	X.XXX
X	-7	XX.X	X.XX	XXX	XXX	XX.X	X.XXX	XXX	XX.X	X.XXX
X	-7	X.XX	X.XX	XXX	XXX	XX.X	X.XXX	XXX	XX.X	X.XXX
X	-7	XXX	X.XX	XXX	XXX	XX.X	X.XXX	XXX	XX.X	X.XXX
n		XX	XX	XX	XX	XX	XX	XX	XX	XX
Mean		XXX.X	X.XXX	XXX.X	XXX.X	XX.XX	X.XXXX	XXX.X	XX.XX	X.XXXX
SD		XX.XX	XX.XX	XX.XX	XX.XX	XX.XX	XX.XX	XX.XX	XX.XX	XX.XX
CV%		XX.X	XX.X	XX.X	XX.X	XX.X	XX.X	XX.X	XX.X	XX.X
SEM		XX.XX	XX.XX	XX.XX	XX.XX	XX.XX	XX.XX	XX.XX	XX.XX	XX.XX
Minimum		XX.X	X.XX	XXX	XXX	XX.X	X.XXX	XXX	XX.X	X.XXX
Median		XX.XX	X.XXX	XXX.X	XXX.X	XX.XX	X.XXXX	XXX.X	XX.XX	X.XXXX
Maximum		XXX	X.XX	XXX	XXX	XX.X	X.XXX	XXX	XX.X	X.XXX

0.25 mg/kg: Single IV Infusion of 0.25 mg/kg xisomab 3G3

0.5 mg/kg: Single IV Infusion of 0.5 mg/kg xisomab 3G3

Placebo = pooled placebo

Fold Change = Post-dialysis / Pre-dialysis

Single IV infusion of 0.25, 0.5 mg/kg xisomab 3G3 or placebo was administered on Day 1

**Programmer Notes:**

Values will be reported at pre- and post-dialysis on Days -7, -5, -3, 1, 3, 5, 6, and 12.

The screening values to be reported if not presented in other tables.

Aronora, Inc.  
xisomab 3G3, Protocol 3G3-18-02  
Celerion, Clinical Study Report No. CA23900

---

For Tables 14.2.4.1.1 through 14.2.4.1.3, Kt/V will be reported on Days -7, -5, -3, 1, 3, 5, and 12. Column titles will be the same as per Table 11-5 shell (ie., R, t, UF, Wt, and Kt/V) with the following footnotes:

- Single IV infusion of 0.25, 0.5 mg/kg xisomab 3G3 or placebo was administered on Day 1
- $R = \text{post-dialysis BUN/pre-dialysis BUN}) * 100$
- t = Time of HD
- $UF = \text{Pre-dialysis Weight} - \text{Post-dialysis Weight}$
- Wt = Post-dialysis weight of patient
- $Kt/V = \ln(R - (0.008 \times t)) + (4 - (3.5 \times R)) \times \frac{UF}{Wt}$

For the bleeding time table in Section 14.3, values will be reported post-dialysis on Days screening (if available), -7, -5, -3, 1, 3, 5, 8, 10 and 12. There will be only one column underneath each dose as per Table 11-4 shell with the following footnote:

- Single IV infusion of 0.25, 0.5 mg/kg xisomab 3G3 or placebo was administered on Day 1

Program: /CAXXXX/sas\_prg/pksas/xxxxxxxx.sas DDMMYYYY HH:MM  
Program: /CAXXXX/sas\_prg/pksas/xxxxxxxx.sas DDMMYYYY HH:MM

Aronora, Inc.  
 xisomab 3G3, Protocol 3G3-18-02  
 Celerion, Clinical Study Report No. CA23900

---

Tables 14.2.6.1 will be in the following format:

Table 14.2.6.1 Summary of Clotting in the Drip Chamber - Days -7 to 12 (Safety Population)

Day	Time Point	0.25 mg/kg Xisomab 3G3					0.5 mg/kg Xisomab 3G3					Pooled Placebo				
		Category*					Category*					Category*				
		1	2	3a	3b	4	1	2	3a	3b	4	1	2	3a	3b	4
Day -7	2 hr after HD	X	X	X	X	X	X	X	X	X	X	X	X	X	X	X
	Post HD	X	X	X	X	X	X	X	X	X	X	X	X	X	X	X
Day X	2 hr after HD	X	X	X	X	X	X	X	X	X	X	X	X	X	X	X
	Post HD	X	X	X	X	X	X	X	X	X	X	X	X	X	X	X

<include all days and timepoints>

Note: \*Category:1=No detectable clotting, 2=Presence of fibrinous ring or minimum clot affecting less than 5% of chamber space,  
 3a=Clot formation (affecting more than 5% of but less than 30% of chamber space) but dialysis still possible,  
 3b=Clot formation (affecting more than 30% of chamber space) but dialysis still possible,  
 4=Complete occlusion of chamber  
 HD: hemodialysis

Program: /AAXXXX/ECR/sas\_prg/stsas/tab\_PROGRAMNAME.sas DDMMYYYY HH:MM

Aronora, Inc.  
 xisomab 3G3, Protocol 3G3-18-02  
 Celerion, Clinical Study Report No. CA23900

---

Tables 14.2.7.1 will be in the following format:

Table 14.2.7.1 Summary of Clotting in the Dialysis Filter - Days -7 to 12 (Safety Population)

Day	0.25 mg/kg Xisomab 3G3					0.5 mg/kg Xisomab 3G3					Pooled Placebo				
	Category*					Category*					Category*				
	1	2	3a	3b	4	1	2	3a	3b	4	1	2	3a	3b	4
Day -7	X	X	X	X	X	X	X	X	X	X	X	X	X	X	X
Day X	X	X	X	X	X	X	X	X	X	X	X	X	X	X	X

<include all days>

Note: \*Category:1= No clotting, clean filter, 2= Few blood streaks (affecting less than 5% of the fibers seen at the surface of dialyzer),  
 3a= More blood streaks (affecting more than 5% but less than 30 % of the fibers seen at the surface of the dialyzer),  
 3b= More blood streaks (affecting more than 30% of the fibers seen at the surface if the dialyzer),  
 4=Complete occlusion

Program: /AAXXXX/ECR/sas\_prg/stsas/tab\_PROGRAMNAME.sas DDMMYYYY HH:MM

Table 14.3.1.1 Treatment-Emergent Adverse Event Frequency by Treatment - Number of Subjects Reporting the Event  
 (% of Subjects Dosed) (Safety Population)

Adverse Event*	Dose Level of Xisomab 3G3		Pooled Placebo	Overall
	0.25 mcg/kg	0.5 mcg/kg		
Number of Subjects Dosed	XX ( XX%)	XX (XXX%)	XX ( XX%)	XX (XXX%)
Number of Subjects With TEAEs^	X ( XX%)	X ( XX%)	X ( XX%)	X ( XX%)
Number of Subjects Without TEAEs^	XX ( XX%)	XX (XXX%)	XX ( XX%)	XX (XXX%)
Nervous system disorders	X ( XX%)	X ( XX%)	X ( XX%)	X ( XX%)
Dizziness	X ( XX%)	X ( XX%)	X ( XX%)	X ( XX%)
Headache	X ( XX%)	X ( XX%)	X ( XX%)	X ( XX%)
Presyncope	X ( XX%)	X ( XX%)	X ( XX%)	X ( XX%)
Respiratory, thoracic and mediastinal disorders	X ( XX%)	X ( XX%)	X ( XX%)	X ( XX%)
Dry throat	X ( XX%)	X ( XX%)	X ( XX%)	X ( XX%)
Oropharyngeal pain	X ( XX%)	X ( XX%)	X ( XX%)	X ( XX%)
Sinus congestion	X ( XX%)	X ( XX%)	X ( XX%)	X ( XX%)
Sneezing	X ( XX%)	X ( XX%)	X ( XX%)	X ( XX%)
General disorders and administration site conditions	X ( XX%)	X ( XX%)	X ( XX%)	X ( XX%)
Fatigue	X ( XX%)	X ( XX%)	X ( XX%)	X ( XX%)
Thirst	X ( XX%)	X ( XX%)	X ( XX%)	X ( XX%)

Note: \*Adverse events are classified according to MedDRA Version 21.1. ^ = Treatment-emergent adverse events  
 If a subject has 2 or more clinical adverse events, the subject is counted only once within a category. The same subject may appear in different categories.

Program: /CAXXXXX/sas\_prg/stsas/tab\_PROGRAMNAME.sas DDMMYYYY HH:MM

Table 14.3.1.2 Treatment-Emergent Adverse Event Frequency by Treatment - Number of Adverse Events  
 (% of Total Adverse Events) (Safety Population)

Adverse Event*	Dose Level of Xisomab 3G3		Pooled Placebo	Overall
	0.25 mg/kg	0.5 mg/kg		
Number of TEAEs	X (100%)	X (100%)	X ( XX%)	X ( XX%)
Nervous system disorders	X ( XX%)	X ( XX%)	X ( XX%)	X ( XX%)
Dizziness	X ( XX%)	X ( XX%)	X ( XX%)	X ( XX%)
Headache	X ( XX%)	X ( XX%)	X ( XX%)	X ( XX%)
Presyncope	X ( XX%)	X ( XX%)	X ( XX%)	X ( XX%)
Respiratory, thoracic and mediastinal disorders	X ( XX%)	X ( XX%)	X ( XX%)	X ( XX%)
Dry throat	X ( XX%)	X ( XX%)	X ( XX%)	X ( XX%)
Oropharyngeal pain	X ( XX%)	X ( XX%)	X ( XX%)	X ( XX%)
Sinus congestion	X ( XX%)	X ( XX%)	X ( XX%)	X ( XX%)
Sneezing	X ( XX%)	X ( XX%)	X ( XX%)	X ( XX%)
General disorders and administration site conditions	X ( XX%)	X ( XX%)	X ( XX%)	X ( XX%)
Fatigue	X ( XX%)	X ( XX%)	X ( XX%)	X ( XX%)
Thirst	X ( XX%)	X ( XX%)	X ( XX%)	X ( XX%)

Note: \*Adverse events are classified according to MedDRA Version 21.1. ^ = Treatment-emergent adverse events

Program: /CAXXXXX/sas\_prg/stsas/tab\_PROGRAMNAME.sas DDMMYYYY HH:MM

Table 14.3.1.3 Treatment-Emergent Adverse Event Frequency by Treatment, Severity, and Relationship to Study Drug -  
 Number of Adverse Events (Safety Population)

Adverse Event*	Dose Level/ Placebo	Number of Subjects With TEAEs	Number of TEAEs	Severity				Relationship to Study Drug				
				Grade 1	Grade 2	Grade 3	Grade 4	Unrelated	Unlikely	Possibly	Probably	Likely
Dizziness	X	X	X	X	X	X	X	X	X	X	X	X
Dry eye	X	X	X	X	X	X	X	X	X	X	X	X
Dry mouth	X	X	X	X	X	X	X	X	X	X	X	X
Dry throat	X	X	X	X	X	X	X	X	X	X	X	X
Ear pain	X	X	X	X	X	X	X	X	X	X	X	X
Fatigue	X	X	X	X	X	X	X	X	X	X	X	X
Headache	X	X	X	X	X	X	X	X	X	X	X	X
Dizziness	X	X	X	X	X	X	X	X	X	X	X	X
Hyperhidrosis	X	X	X	X	X	X	X	X	X	X	X	X
Laceration	X	X	X	X	X	X	X	X	X	X	X	X
Limb crushing injury	X	X	X	X	X	X	X	X	X	X	X	X
Muscle twitching	X	X	X	X	X	X	X	X	X	X	X	X
0.25 mg/kg		X	X	X	X	X	X	X	X	X	X	X
0.5 mg/kg		X	X	X	X	X	X	X	X	X	X	X
Placebo		XX	XX	X	X	X	X	X	X	X	X	X
Overall		XX	XX	X	X	X	X	X	X	X	X	X

Note: 0.25 mg/kg: Single IV Infusion of 0.25 mg/kg xisomab 3G3

0.5 mg/kg: Single IV Infusion of 0.5 mg/kg xisomab 3G3

Placebo = pooled placebo

\*Adverse events are classified according to MedDRA Version 21.1. TEAE = Treatment-emergent adverse events

If a subject experience the same adverse event (AE) at more than one level of severity during a treatment, each AE is counted separately. If a subject experience the same AE at more than one level of drug relationship during a treatment, each AE is counted separately.

Severity: Grade 1 = Mild; Grade 2 = Moderate; Grade 3 = Severe; Grade 4 = Potentially life-threatening

Program: /CAXXXXX/sas\_prg/stsas/tab\_PROGRAMNAME.sas DDMMYYYY HH:MM

Aronora, Inc.  
 xisomab 3G3, Protocol 3G3-18-02  
 Celerion, Clinical Study Report No. CA23900

---

Tables 14.3.4.1 to 14.3.4.3 will have the following format:

Page 1 of X

Table 14.3.4.1 Out-of-Range Values and Clinically Significant Results - Serum Chemistry (Safety Population)

Dose Level/ Placebo	Subject Number	Age#/ Sex	Study Period	Day	Hour	Date	Time	Parameter1 <Range> (Unit)	Parameter2 <Range> (Unit)	Parameter3 <Range> (Unit)	Parameter4 <Range> (Unit)	Parameter5 <Range> (Unit)
XXX <units>	X	XX/X	Screen	.	.	DDMMYYYY	HH:MM:SS	XX H +				XX L
			1	-X	-XX.XX	DDMMYYYY	HH:MM:SS	XX L	XX L	XX H	XX L	
			Recheck			DDMMYYYY	HH:MM:SS				XX	

Programmer Notes: Replace Parameter1, 2 etc. with actual lab tests in the study. Sort unscheduled assessment and early termination chronologically with other scheduled assessments.

Note: 0.25 mg/kg: Single IV Infusion of 0.25 mg/kg xisomab 3G3  
 0.5 mg/kg: Single IV Infusion of 0.5 mg/kg xisomab 3G3  
 Placebo = pooled placebo  
 #Age is calculated at the time of first dosing. F = Female; M = Male  
 H = Above reference range, L = Below reference range  
 PI Interpretation: + = Clinically significant

Program: /CAXXXXX/sas\_prg/stsas/tab\_PROGRAMNAME.sas DDMMYYYY HH:MM

Tables 14.3.5.1, 14.3.5.3 and 14.3.5.5 will be in the following format:

Table 14.3.5.1 Clinical Laboratory Summary and Change from Baseline - Serum Chemistry (Safety Population)

Laboratory Test (unit)	Reference Range	Time Point	Statistic	Change from Baseline*					
				0.25 mg/kg	0.5 mg/kg	Placebo	0.25 mg/kg	0.5 mg/kg	Placebo
XXXXXXXX (unit)	X.X-XX.X#	Screen	n	XX	XX	XX			
			Mean	X.XX	X.XX	X.XX			
			SD	X.XXX	X.XXX	X.XXX			
			Minimum	X.XX	X.XX	X.XX			
			Median	X.X	X.X	X.X			
			Maximum	XX.X	XX.X	XX.X			
		Baseline*	n	XX	XX	XX			
			Mean	X.XX	X.XX	X.XX			
			SD	X.XXX	X.XXX	X.XXX			
			Minimum	X.XX	X.XX	X.XX			
			Median	X.X	X.X	X.X			
			Maximum	XX.X	XX.X	XX.X			
		Day X, Hour X.XX	n	XX	XX	XX	XX	XX	XX
			Mean	X.XX	X.XX	X.XX	X.XX	X.XX	X.XX
			SD	X.XXX	X.XXX	X.XXX	X.XXX	X.XXX	X.XXX
			Minimum	X.XX	X.XX	X.XX	X.XX	X.XX	X.XX
			Median	X.X	X.X	X.X	X.X	X.X	X.X
			Maximum	XX.X	XX.X	XX.X	XX.X	XX.X	XX.X

<include all timepoints>

**Programmer Note:** Table 14.3.5.5 will not include timepoints that are summarized in PD endpoint tables in 14.2.

Note: 0.25 mg/kg: Single IV Infusion of 0.25 mg/kg xisomab 3G3

0.5 mg/kg: Single IV Infusion of 0.5 mg/kg xisomab 3G3

Placebo = pooled placebo

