## 7.2 Data Summarization and Presentation of PD Parameters

### 7.2.1 aPTT

**Sample Collection:** Samples for the coagulation parameter (aPTT) will be collected at screening, pre- and post-dialysis on Days -7, -5, -3, 1, 3, 5, and 12. Additional samples for aPTT will be collected following xisomab 3G3/placebo dosing on Day 1 at predose (hour 0, at least 1 hour prior the start of HD session) and at 0.167, 0.5, 1, 2, 3, 4, 6, 8, 12, 16, 24, 48, 96, 120, 144, and 192, hours after xisomab 3G3 start of infusion.

**Baseline Calculation Method Following Day 1 Dosing:** Following xisomab 3G3 dosing on Day 1, aPTT change from baseline will be calculated by dividing postdose aPTT values from average of pre-dose baseline (the average of pre-dialysis aPTT values on Days -7, -5, -3, and 1 will be calculated as pre-dose baseline).

**Fold change in aPTT values:** The fold change in aPTT values on Days -7, -5, -3, 1 (only pre- and post-dialysis aPTT values on Day 1), 3, 5, and 12 will be calculated by dividing the post-dialysis aPTT/pre-dialysis aPTT values for each day separately.

aPTT values will be extracted from the clinical laboratory database and descriptive statistics will be generated using SAS® version 9.3 or higher. Following Day 1 xisomab 3G3 dosing, a table will be presented for the aPTT change from baseline with descriptive statistics.

aPTT values will be listed and summarized by treatment and time points in Tables and Figures for all subjects in the Safety Population (2 active dose levels and pooled placebo). aPTT values will be presented with the same level of precision as received from the clinical laboratory database. Summary statistics, including n, Mean, SD, CV%, SEM, minimum, median, and maximum will be calculated for all nominal values time points. Excluded subjects will be included in the aPPT values tables, but will be excluded from the summary statistics and noted as such in the tables.

Mean and individual aPTT values-time and change from baseline-time profiles will be presented on linear scale. Linear mean plots will be presented with and without SD.

The level of precision for the aPPT values summary statistic will be presented as follows:

- minimum/maximum: in same precision as in the clinical laboratory database
- Mean/median: in one more level of precision than minimum/maximum
- SD/SEM: in one more level of precision than Mean/median
- n will be presented as an integer
- CV% will be presented to the nearest tenth

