## **8.4 Clinical Laboratory Tests (Serum Chemistry, Hematology, Coagulation and Urinalysis)**

Safety serum chemistry, hematology and urinalysis tests are performed at Screening, Day -8 check-in, Day 1 predose, Day 6 and Day 12. For anuric patients, urinalysis may not be performed. Platelet count are collected at start and end of HD on Days -7, -5, -3, 1, 3, 5 and 12 and on Day 6. Platelet count are collected at start and end of HD on Days -7, -5, -3, 1, 3, 5 and 12 and Day 6. aPTT results are presented and discussed in the PD Section 7.2.

Out-of-range values and clinically significant results will be listed.

For all numeric laboratory values, descriptive statistics will be presented for each laboratory test by assessment time point and treatment. Change from baseline will be summarized in a similar manner. Baseline is defined as the result closest and prior to

dose which may include unscheduled results. This will typically be the result collected at predose on Day 1. Postdose unscheduled events or early termination results will not be included in summaries.

For each laboratory test, a shift table will be developed to compare the frequency of the results at baseline (above normal, normal, or below normal) with the respective postdose results.

Coagulation parameters and platelet count will be listed and presented together since they have the same timepoints. Urinalysis test results will be listed only.

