**Notes for Generating the Actual Table:**

- n will be presented as an integer (with no decimal);
- Summary statistics will be presented with same precision as defined in post-text shells
- Internal template ITPar1, with the following changes: n will be presented in the column title with additional columns to be created.

For Table 12-2 through 12-5 the source tables will be 14.3.5.5

Program: /CAXXXXX/sas\_prg/pksas/intext-pk-tables.sas DDMMYYYY HH:MM  
 Program: /CAXXXXX/sas\_prg/pksas/adam\_intext\_pkparam.sas DDMMYYYY HH:MM

Table 11-5 Summary of Kt/V Values (Safety Population)

Time Point	Single pool Kt/V														
	Treatments														
	Single IV Infusion of 0.25 mg/kg xisomab 3G3					Single IV Infusion of 0.5 mg/kg xisomab 3G3					Placebo (Pooled)				
	R (unit) [n=xx]	t (unit) [n=xx]	UF (unit) [n=xx]	Wt (unit) [n=xx]	Kt/V (unit) [n=xx]	R (unit) [n=xx]	t (unit) [n=xx]	UF (unit) [n=xx]	Wt (unit) [n=xx]	Kt/V (unit) [n=xx]	R (unit) [n=xx]	t (unit) [n=xx]	UF (unit) [n=xx]	Wt (unit) [n=xx]	Kt/V (unit) [n=xx]
Day -7	XX.X	XX.X	XX.X	XX.X	XX.X	XX.X	XX.X	XX.X	XX.X	XX.X	XX.X	XX.X	XX.X	XX.X	XX.X
Day -5	XX.X	XX.X	XX.X	XX.X a	XX.X	XX.X	XX.X	XX.X	XX.X	XX.X	XX.X	XX.X	XX.X	XX.X	XX.X
Day -3	XX.X	XX.X	XX.X	XX.X	XX.X	XX.X	XX.X	XX.X	XX.X	XX.X	XX.X	XX.X	XX.X	XX.X	XX.X
Day 1*	XX.X	XX.X	XX.X	XX.X	XX.X	XX.X	XX.X	XX.X	XX.X	XX.X	XX.X	XX.X	XX.X	XX.X	XX.X
Day 3	XX.X	XX.X	XX.X	XX.X	XX.X	XX.X	XX.X	XX.X	XX.X	XX.X	XX.X	XX.X	XX.X	XX.X	XX.X
Day 5	XX.X	XX.X	XX.X	XX.X	XX.X	XX.X	XX.X	XX.X	XX.X	XX.X	XX.X	XX.X	XX.X	XX.X	XX.X
Day 12	XX.X	XX.X	XX.X	XX.X	XX.X	XX.X	XX.X	XX.X	XX.X	XX.X	XX.X	XX.X	XX.X	XX.X	XX.X

a-n=xx  
 \* - Single IV infusion of 0.25, 0.5 mg/kg xisomab 3G3 or placebo was administered on Day 1  
 Values will be presented as arithmetic mean

R= post-dialysis BUN/pre-dialysis BUN)\*100  
 t = Time of HD  
 UF = Pre-dialysis Weight – Post-dialysis Weight  
 Wt = Post-dialysis weight of patient  

$$Kt/V = \ln(R - (0.008 \times t)) + (4 - (3.5 \times R)) \times \frac{UF}{Wt}$$

Source: Tables 14.2.4.1.1 through 14.2.4.1.3  
 Program: /CAXXXX/sas prg/stsas/intext/t ac.sas DDMMYYYY HH:MM

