# = Lowest of the lower ranges and highest of the higher ranges are used. Refer to Appendix 16.1.10.1 for the breakdown.

\* Baseline is defined as the result closest and prior to dose on Day 1.

**Programmer note:** for PT, INR and PT/INR, the pre-dialysis value will be the baseline value for that day and the "change from baseline" will be the fold change from baseline "ie. Post-dialysis / Pre-dialysis.

Program: /AAXXXXX/ECR/sas\_prg/stsas/tab\_PROGRAMNAME.sas DDMMYYYY HH:MM

Tables 14.3.5.2, 14.3.5.4 and 14.3.5.6 will be in the following format:

Table 14.3.5.2 Clinical Laboratory Shift From Baseline - Serum Chemistry (Safety Population)

Laboratory Test (unit)	Dose Level/ Placebo	Time Point	Baseline* L			Baseline* N			Baseline* H		
			L	N	H	L	N	H	L	N	H
XXXXXXX (unit)	XXX <units>	Day X, Hour X.XX	X	XX	X	X	XX	X	X	XX	X

**Programmer Note:** Table 14.3.5.6 will not include timepoints that are summarized in PD endpoint tables in 14.2.

Note: 0.25 mg/kg: Single IV Infusion of 0.25 mg/kg xisomab 3G3  
 0.5 mg/kg: Single IV Infusion of 0.5 mg/kg xisomab 3G3  
 Placebo = pooled placebo  
 N = Within Normal Range, L = Below Normal Range, H = Above Normal Range  

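### Programmer notes to SAP Tables 14.3.5.5 and 14.3.5.6 exclude time points where they should exclude aPTT results; read literally, they remove platelet summaries and coagulation/platelet shifts by arm

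*SAP*

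**What the plan says.** Two programmer notes in SAP section 11.3 are at issue. Under the shell shared by Tables 14.3.5.1, 14.3.5.3 and 14.3.5.5: "Table 14.3.5.5 will not include timepoints that are summarized in PD endpoint tables in 14.2". Under the shift-table shell: "Table 14.3.5.6 will not include timepoints that are summarized in PD endpoint tables in 14.2". SAP 10.2 titles both affected tables as covering coagulation and platelet count.

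On the schedule, SAP 8.4 states: "Platelet count are collected at start and end of HD on Days -7, -5, -3, 1, 3, 5 and 12 and on Day 6". It adds: "Coagulation parameters and platelet count will be listed and presented together since they have the same timepoints". SAP 7.2.1 has aPTT collected "pre- and post-dialysis on Days -7, -5, -3, 1, 3, 5, and 12", with further serial samples that include 120 hours. The note to aPTT Tables 14.2.5.1.7 to 14.2.5.1.9 reads: "Values will be reported at pre- and post-dialysis on Days -7, -5, -3, 1, 3, 5, 6, and 12".

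SAP 8.4 also asks for descriptive statistics for every numeric laboratory test by time point and treatment, and for a shift table for each test. The only result it sends to the PD section is aPTT. Protocol 14.3.1 likewise plans laboratory summaries by treatment and collection time, plus a shift table.

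Three instructions in the shells point the other way for PT/INR in Table 14.3.5.5:
- Below the same shell, "for PT, INR and PT/INR, the pre-dialysis value will be the baseline value for that day", with a post-/pre-dialysis fold change.
- The shell carries a placeholder asking for all time points.
- In SAP 11.1, "For Table 12-2 through 12-5 the source tables will be 14.3.5.5". Tables 12-2 to 12-4 are the in-text PT, INR and PT/INR tables for Days -7 to 12.

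**The concern.** The apparent purpose of the notes is to avoid printing aPTT twice. Their wording does something else: it removes a row because its time point appears in a 14.2 table, whichever test the row belongs to. Platelet count, PT and INR share the aPTT schedule, so they would go too, and no 14.2 table reports them. The 14.2 tables cover PK, BUN/URR, potassium, Kt/V, aPTT and clotting grades.

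Changes in clinical laboratory evaluations are part of the primary outcome (Protocol 9.2, SAP 2.2). Protocol 8.5 says the hemostatic safety of the drug in this population is not yet known, and all sessions are heparin-free. Platelet count and PT/INR around dialysis are therefore readings that a safety reviewer would want compared by arm. SAP section 9 states that the analyses are aligned with the protocol, so the omission is not a declared change.

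**Working it through.** The plan gives no figure to reproduce and no power or alpha calculation is involved. The check compares two schedules.

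**Inputs.** Platelet and PT/INR schedule: SAP 8.4. aPTT time points in 14.2: SAP 7.2.1 (pre- and post-dialysis samples and the 120-hour sample) and the note to Tables 14.2.5.1.7 to 14.2.5.1.9 (which names Day 6).

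**Count.** On-study time points = 7 dialysis days × 2 + Day 6 = 14 + 1 = 15.

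| Time point | Platelets, PT/INR | Also in aPTT tables | Left after the note |
|---|---|---|---|
| Days -7, -5, -3, pre and post | 6 | 6 | 0 |
| Day 1 pre | 1 | 1 | 0 |
| Day 1 post | 1 | 1 | 0 |
| Day 3 pre and post | 2 | 2 | 0 |
| Day 5 pre and post | 2 | 2 | 0 |
| Day 6 | 1 | 1 | 0 |
| Day 12 pre and post | 2 | 2 | 0 |
| **All on-study** | **15** | **15** | **0** |
| **Post-dose** (1 + 2 + 2 + 1 + 2) | **8** | **8** | **0** |

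Day 6 is not a dialysis day, so the pre-/post-dialysis wording of the aPTT note does not fit it. If Day 6 were not counted as a 14.2 time point, 1 of 8 post-dose rows would remain. It should be counted, because the 120-hour aPTT sample falls there and the note names the day.

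**Effect by test and table, notes read literally.**
- *Platelets, Table 14.3.5.5:* 0 of 8 post-dose rows. The Day 1 pre-dialysis value also coincides with aPTT, so at most a screening row is left. Apart from the general all-time-points placeholder, no shell instruction calls for these rows.
- *Platelets, PT and INR, shift Table 14.3.5.6:* 0 of 8 post-dose rows. No other shell note restores them.
- *PT/INR, Table 14.3.5.5:* the exclusion gives 0 of 8, but the fold-change note, the all-time-points placeholder and the source for Tables 12-2 to 12-4 all need the rows. The instructions cannot all be followed.
- *aPTT, Table 14.3.5.6:* the normal-range shift is removed as well, and no 14.2 table supplies one.

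**What could survive elsewhere.** Protocol 13.2.7 lists platelet count under hematology, and SAP 8.4 schedules post-dose hematology on Day 6 and Day 12. Platelets at those visits could appear in Tables 14.3.5.3 and 14.3.5.4, which carry no exclusion; the SAP does not say whether they will. Between dosing and 120 hours there are 1 + 2 + 2 = 5 platelet time points (Day 1 post, Day 3 pre and post, Day 5 pre and post), and none has another by-arm table.

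**After correction.** With the notes limited to aPTT, all 8 post-dose time points stay in both tables for PT, INR and platelets.

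**The case against.** The best reply is that nobody would program the notes this way. The shell is arranged by laboratory test and then by time point, so the note can be read as dropping a test's results where that same test is already summarized in 14.2. Among these tests only aPTT is. The literal reading nearly empties one planned table and wholly empties the other. SAP 8.4 states the intent, and section 11 describes the shells as a general layout that may change. A literal programmer could not build Tables 12-2 to 12-4, so the slip would probably surface before reporting.

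Much of this stands. The intent was very likely to omit aPTT only. The analyses are descriptive, no test or interim rule depends on these tables, and they can be regenerated. Out-of-range values are tabulated (Table 14.3.4.2), and a programmer note in section 12 requires all coagulation and platelet time points to be listed with flags. With 9 to 12 patients per cohort at 2:1, each active arm has 6 to 8 patients, so the listings are readable.

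The reply does not remove the defect. The notes name time points, not aPTT. Tables 12-2 to 12-4 would expose the PT/INR conflict, but no in-text table depends on platelet counts or on the shift table, so those omissions could pass unnoticed. The allowance for shell changes refers to unforeseen circumstances, and this conflict is visible now. Listings are not by-arm summaries or shifts.

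**Conclusion.** The concern holds as a wording error with a defined reach. Read literally, the notes remove platelet count from the Table 14.3.5.5 summary, and PT, INR and platelet count from the Table 14.3.5.6 shifts, at all 8 post-dose time points. Only Day 6 and Day 12 platelets might still appear, in the hematology tables. For PT/INR in Table 14.3.5.5 the SAP contains an unresolved contradiction. Both notes also conflict with SAP 8.4.

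A reader might infer that PT/INR lose every post-dose row in the safety summary, or that safety data disappear from the report. The documents support neither inference. Three shell instructions call for the PT/INR rows, Tables 12-2 to 12-4 are planned as by-arm summaries, and the listings keep every value.

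The conclusion assumes that the notes are applied as written and that Day 6 counts as a time point in the aPTT tables. Priority is moderate: the displays are descriptive and the error is probably a slip, but they belong to the primary safety outcome and the instruction as it stands is wrong.

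**What to change.** Reword both notes along these lines: *aPTT summary statistics already shown in 14.2 are not repeated here. PT, INR and platelet count are summarized in Table 14.3.5.5 at every scheduled time point (before and after HD on Days -7, -5, -3, 1, 3, 5 and 12, and on Day 6), and shifts are given in Table 14.3.5.6 for the post-dose ones. The aPTT normal-range shift is retained in Table 14.3.5.6.*

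The last sentence is needed because SAP 8.4 asks for a shift table for each test and 14.2 has none for aPTT. The change is confined to the two notes and needs no new data or analysis method. The cost is longer tables. It should be made before unblinding, so that the choice of rows cannot depend on the results.
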